12.4. Dissemination of Clinical Study Data

The Sponsor fulfills its commitment to publicly disclose clinical study results through posting the results of studies on www.clinicaltrials.gov (ClinicalTrials.gov), the EudraCT/CTIS, and/or www.pfizer.com, and other public registries and websites in accordance with applicable local laws/regulation. In addition, the Sponsor reports study results outside of the requirement of local laws/regulations pursuant to its standard operating procedures.

In all cases, study results are reported by the Sponsor in an objective, accurate, balanced, and complete manner and are reported regardless of the outcome of the study or the country in which the study was conducted.

www.clinicaltrials.gov

The Sponsor posts clinical trial results on www.clinicaltrials.gov for GBT/Pfizer sponsored interventional studies (conducted in patients) that evaluate the safety and/or efficacy of a product, regardless of the geographical location in which the study is conducted. These results are submitted for posting in accordance with the format and timelines set forth by US law.

EudraCT/CTIS

The Sponsor posts clinical trial results on EudraCT/CTIS for GBT/Pfizer sponsored interventional studies in accordance with the format and timelines set forth by EU requirements.

www.pfizer.com

The Sponsor posts clinical study report (CSR) synopses and plain-language study results summaries on www.pfizer.com for GBT/Pfizer sponsored interventional studies at the same time the corresponding study results are posted to www.clinicaltrials.gov. CSR synopses will have personally identifiable information anonymized.

Documents within marketing applications

The Sponsor complies with applicable local laws/regulations to publish clinical documents included in marketing applications. Clinical documents include summary documents and CSRs including the protocol and protocol amendments, sample CRFs, and SAPs. Clinical documents will have personally identifiable information anonymized.

090177e19fbdcff7\Approved\Approved On: 24-Jan-2024 21:35 (GMT)

Data sharing

The Sponsor provides researchers secure access to participant-level data or full CSRs for the purposes of "bona fide scientific research" that contributes to the scientific understanding of the disease, target, or compound class. The Sponsor will make data from these trials available 18 months after study completion. Participant level data will be anonymized in accordance with applicable privacy laws and regulations. CSRs will have personally identifiable information anonymized.

Data requests are considered from qualified researchers with the appropriate competencies to perform the proposed analyses. Research teams must include a biostatistician. Data will not be provided to applicants with significant conflicts of interest, including individuals requesting access for commercial/competitive or legal purposes.

12.5. Data Quality Assurance

All participant data relating to the study will be recorded on printed or electronic CRF unless transmitted to the Sponsor or designee electronically (eg, laboratory data). The Investigator is responsible for verifying that data entries are accurate and correct by physically or electronically signing the CRF.

Guidance on completion of CRFs will be provided in the CRF Completion Requirement document.

The Investigator must ensure that the CRFs are securely stored at the study site in encrypted electronic and/or paper form and are password-protected or secured in a locked room to prevent access by unauthorized third parties.

The Investigator must permit study-related monitoring, audits, IRB/EC review, and regulatory agency inspections and provide direct access to source records and documents. This verification may also occur after study completion. It is important that the Investigator(s) and their relevant personnel are available during the monitoring visits and possible audits or inspections and that sufficient time in devoted to the process.

Monitoring details describing strategy, including definition of study-critical data items and processes (eg, risk-based initiatives in operations and quality such as risk management and mitigation strategies and analytical risk-based monitoring), methods, responsibilities, and requirements, including handling of noncompliance issues and monitoring techniques (central, virtual, or on-site monitoring), are provided in the data management plan maintained and utilized by the Sponsor or designee.

The Sponsor or designee is responsible for the data management of this study, including quality checking of the data.

Records and documents, including signed ICFs, pertaining to the conduct of this study must be retained by the Investigator for 15 years after study completion unless local regulations or institutional policies require a longer retention period. No records may be destroyed during the retention period without the written approval of the sponsor. No records may be transferred to another location or party without written notification to the Sponsor. The Investigator must ensure that the records continue to be stored securely for as long as they are maintained.

When participant data are to be deleted, the Investigator will ensure that all copies of such data are promptly and irrevocably deleted from all systems.

The Investigator(s) will notify the Sponsor or its agents immediately of any regulatory inspection notification in relation to the study. Furthermore, the Investigator will cooperate with the Sponsor or its agents to prepare the Investigator site for the inspection and will allow the Sponsor or its agent, whenever feasible, to be present during the inspection. The Investigator site and Investigator will promptly resolve any discrepancies that are identified between the study data and the participant's medical records. The Investigator will promptly provide copies of the inspection findings to the Sponsor or its agent. Before response submission to the regulatory authorities, the Investigator will provide the Sponsor or its agents with an opportunity to review and comment on responses to any such findings.

12.6. Study and Site Start and Closure

The study start date is the date of the first participant's first visit.

The Sponsor designee reserves the right to close the study site or terminate the study at any time for any reason at the sole discretion of the Sponsor, including (but not limited to) regulatory authority decision, change in opinion of the IRB/EC, or change in benefit-risk assessment. Study sites will be closed upon study completion. A study site is considered closed when all required documents and study supplies have been collected and a study-site closure visit has been performed.

The Investigator may initiate study-site closure at any time upon notification to the Sponsor or designee/CRO if requested to do so by the responsible IRB/EC or if such termination is required to protect the health of study participants.

Reasons for the early closure of a study site by the Sponsor may include but are not limited to:

- Failure of the Investigator to comply with the protocol, the requirements of the IRB/EC or local health authorities, the Sponsor's procedures, or the ICH GCP guidelines;
- Inadequate recruitment of participants by the Investigator;
- Discontinuation of further study intervention development.

If the study is prematurely terminated or suspended, the Sponsor shall promptly inform the Investigators, the ECs/IRBs, the regulatory authorities, and any CRO(s) used in the study of the reason for termination or suspension, as specified by the applicable regulatory requirements. The Investigator shall promptly inform the participant and should assure appropriate participant therapy and/or follow-up.

Study termination is also provided for in the clinical study agreement. If there is any conflict between the contract and this protocol, the contract will control as to termination rights.

13. PUBLICATION POLICY

For multicenter trials, the primary publication will be a joint publication developed by the Investigator and the Sponsor reporting the primary endpoint(s) of the study covering all study sites. The Investigator agrees to refer to the primary publication in any subsequent publications. The Sponsor will not provide any financial compensation for the Investigator's participation in the preparation of the primary congress abstract, poster, presentation, or primary manuscript for the study.

Investigators are free to publish individual center results that they deem to be clinically meaningful after publication of the overall results of the study or 12 months after primary completion date or study completion at all sites, whichever occurs first, subject to the other requirements described in this section.

The Investigator will provide the Sponsor an opportunity to review any proposed publication or any other type of disclosure of the study results (collectively, "publication") before it is submitted or otherwise disclosed and will submit all publications to the Sponsor 30 days before submission. If any patent action is required to protect intellectual property rights, the Investigator agrees to delay the disclosure for a period not to exceed an additional 60 days upon request from the Sponsor. This allows the Sponsor to protect proprietary information and to provide comments, and the Investigator will, on request, remove any previously undisclosed confidential information before disclosure, except for any study intervention or Sponsor related information necessary for the appropriate scientific presentation or understanding of the study results. For joint publications, should there be disagreement regarding interpretation and/or presentation of specific analysis results, resolution of, and responsibility for, such disagreements will be the collective responsibility of all authors of the publication.

For all publications relating to the study, the investigator and the Sponsor will comply with recognized ethical standards concerning publications and authorship, including those established by the International Committee of Medical Journal Editors. The Investigator will disclose any relationship with the Sponsor and any relevant potential conflicts of interest, including any financial or personal relationship with the Sponsor, in any publications. All authors will have access to the relevant statistical tables, figures, and reports (in their original format) required to develop the publication.

15. APPENDICES

Appendix 1. Schedule of assessments

Assessments			Tre	eatment I	Period					End of Studyi
Study Day(s)	Day 1ª	W4* ± 5 days	W8* ± 5 days	W12 ± 5 days	W24 ± 10 days	W36 ± 10 days	W48 ± 10 days	Q12 Wks ± 10 days	Q24 Wks ± 10 days	
Informed Consent/Assent	X							unjs	unjs	
Eligibility Assessment	X									
Medical History	X									
Physical Examination b	X	X	X	X	X		X		X	X
Vital Signs ^c	X	X	X	X	X		X			X
Adverse Events	X	X	X	X	X		X		X	X
Concomitant Medications	X	X	X	X	X		X		X	X
Hematology/Chemistry analyzed by Central Laboratory (US and Europe only) ^d	X	X	X	X	X		X			X
Hematology/Chemistry analyzed by Local Laboratory (ex-US and ex-Europe only) ^{d, e}	Xª	X	X	X	X		X		X f	Х
Exploratory Laboratory CCI (US and Europe Only)	X			X	X		X			
Urine Pregnancy Test ^g	X	X	X	X	X		X		X	X
Drug Dispensing and Accountability ^h	X			X	X	X	X	X	X	Х

Assessments		Treatment Period							End of Studyi	
Study Day(s)	Day	W4*	W8*	W12	W24	W36	W48	Q12	Q24	
	1ª	± 5	± 5	± 5	± 10	± 10	± 10	Wks	Wks	
		days	days	days	days	days	days	± 10	± 10	
								days	days	

Amendment 3

Abbreviations: Q = every; W = week; Wks = weeks

- * Participants from GBT440-031 who received GBT440 900 mg or placebo, or who received voxelotor for less than 12 weeks will have additional assessments at Week 4 and Week 8.
- a. Eligibility assessments will be determined on Day 1 prior to dosing. If labs were done for GBT440-031 or this study within 7 days of Day 1, they do not need to be repeated on Day 1.
- Abbreviated Physical Exam which includes: general appearance, examination of eyes, skin, cardiovascular and respiratory systems, an abdominal examination and a symptom directed examination.
- c. Vital signs (heart rate [HR], blood pressure [BP]) will be collected after a participant has rested for at least 5 minutes in the seated or supine position. A repeated measurement of HR and BP will be taken if the first reading is outside the normal range and deemed clinically significant.
- d. Hematology assessments will include: red blood cell (RBC), hematocrit (Hct), hemoglobin (Hb), platelets, white blood cell (WBC), we reticulocytes, absolute reticulocytes, RBC distribution width (RDW), mean corpuscular volume (MCV) and mean corpuscular hemoglobin concentration (MCHC). After Week 48, hematology assessments should only be performed per standard of care.
- e. Serum chemistries will include: Alanine aminotransferase (ALT), alkaline phosphatase (ALK), aspartate aminotransferase (AST), bicarbonate, BUN, creatinine, LDH, sodium, potassium, bilirubin (total, direct, and indirect). After Week 48, serum chemistries should only be performed per standard of care.
- f. After Week 48 (for participants enrolled outside of the United States and Europe), laboratory values for measures of hemolysis such as hemoglobin, % reticulocytes, absolute reticulocytes, and bilirubin (total, direct, and indirect) will be collected every 24 weeks.
- g. If a urine pregnancy test is positive, the result must be confirmed per local standard of care (eg. ultrasound or serum pregnancy test).
- h. Voxelotor will be dispensed in 12-week (~90 day) intervals with instruction to participants to return any used/unused bottles to clinic.
- The End of Study (EOS) visit should be conducted within 28-35 days after last dose of study drug for participants who withdraw from the study early.

The EOS visit can occur any time after participants obtains commercial voxelotor for participants who complete study per protocol. Participants who complete study per protocol should remain on study drug until EOS visit is completed.

Appendix 2. LIVER SAFETY: SUGGESTED ACTIONS AND FOLLOW UP ASSESSMENTS

Potential Cases of Drug Induced Liver Injury

Humans exposed to a drug who show no sign of liver injury (as determined by elevations in transaminases) are termed "tolerators," while those who show transient liver injury but adapt are termed "adaptors." In some participants, transaminase elevations are a harbinger of a more serious potential outcome. These participants fail to adapt and therefore are "susceptible" to progressive and serious liver injury, commonly referred to as DILI. Participants who experience a transaminase elevation above 3 × the upper limit of normal (ULN) should be monitored more frequently to determine if they are "adaptors" or are "susceptible."

Liver function tests (LFTs) are not required as a routine safety monitoring procedure in this study. However, should an investigator deem it necessary to assess LFTs because a participant presents with clinical signs/symptoms, such LFT results should be managed and followed as described below.

In the majority of DILI cases, elevations in AST (aspartate transaminase) and/or ALT (alanine transaminase) precede total bilirubin elevations (> 2 × ULN) by several days or weeks. The increase in total bilirubin typically occurs while AST/ALT is/are still elevated above 3 × ULN (ie, AST/ALT and total bilirubin values will be elevated within the same laboratory sample). In rare instances, by the time total bilirubin elevations are detected, AST/ALT values might have decreased. This occurrence is still regarded as a potential DILI. Therefore, abnormal elevations in either AST or ALT in addition to total bilirubin that meet the criteria outlined below are considered potential DILI (assessed per Hy's law criteria) cases and should always be considered important medical events, even before all other possible causes of liver injury have been excluded.

The threshold of laboratory abnormalities for a potential DILI case depends on the participant's individual baseline values and underlying conditions. Participants who present with the following laboratory abnormalities should be evaluated further as potential DILI (Hy's law) cases to definitively determine the etiology of the abnormal laboratory values:

- Participants with AST/ALT and total bilirubin values within the normal range who subsequently present with AST/ALT values ≥ 3 × ULN AND a total bilirubin value ≥ 2 × ULN with no evidence of hemolysis and an alkaline phosphatase value < 2 × ULN or not available.
- For participants with baseline AST OR ALT OR total bilirubin values above the ULN, the following threshold values are used in the definition mentioned above, as needed, depending on which values are above the ULN at baseline:
 - Preexisting AST/ALT baseline values above the normal range: AST/ALT values ≥ 2 times the baseline values AND ≥ 3 × ULN; or ≥ 8 × ULN (whichever is smaller).

 Preexisting values of total bilirubin above the normal range: total bilirubin level increased from baseline value by an amount of ≥ 1 × ULN or if the value reaches ≥ 3 × ULN (whichever is smaller).

Rises in AST/ALT and total bilirubin separated by more than a few weeks should be assessed individually based on clinical judgment; any case where uncertainty remains as to whether it represents a potential Hy's law case should be reviewed with the sponsor.

The participant should return to the investigator site and be evaluated as soon as possible, preferably within 48 hours from awareness of the abnormal results. This evaluation should include laboratory tests, detailed history, and physical assessment.

In addition to repeating measurements of AST and ALT and total bilirubin for suspected Hy's law cases, additional laboratory tests should include albumin, creatine kinase, direct and indirect bilirubin, gamma-glutamyl transferase, prothrombin time/international normalized ratio, eosinophils (%), and alkaline phosphatase. Consideration should also be given to drawing a separate tube of clotted blood and an anticoagulated tube of blood for further testing, as needed, for further contemporaneous analyses at the time of the recognized initial abnormalities to determine etiology. A detailed history, including relevant information, such as review of ethanol, acetaminophen/paracetamol (either by itself or as a coformulated product in prescription or over-the-counter medications), recreational drug, or supplement (herbal) use and consumption, family history, sexual history, travel history, history of contact with a jaundiced person, surgery, blood transfusion, history of liver or allergic disease, and potential occupational exposure to chemicals, should be collected. Further testing for acute hepatitis A, B, C, D, and E infection, total bile acids, liver imaging (eg, biliary tract), and collection of serum samples for acetaminophen/paracetamol drug and/or protein adduct levels may be warranted.

All cases demonstrated on repeat testing as meeting the laboratory criteria of AST/ALT and total bilirubin elevation defined above should be considered potential DILI (Hy's law) cases if no other reason for the LFT abnormalities has yet been found. Such potential DILI (Hy's law) cases are to be reported as SAEs, irrespective of availability of all the results of the investigations performed to determine etiology of the LFT abnormalities.

A potential DILI (Hy's law) case becomes a confirmed case only after all results of reasonable investigations have been received and have excluded an alternative etiology.

Document Approval Record

Document Name: GBT440-034_C5341022 PA3_18 December 2023_clean

Document Title: GBT440-034_C5341022 PA3_18 December 2023_clean

Signed By:	Date(GMT)	Signing Capacity
PPD	24-Jan-2024 16:09:37	Manager Approval
PPD	24-Jan-2024 21:35:33	Final Approval

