1. BACKGROUND INFORMATION

Sickle Cell Disease (SCD) is a rare, devastating, and debilitating disease marked by the pathophysiologic features of hemolytic anemia, vaso-occlusion, and progressive end-organ damage, with a clinical course characterized by life-long disability and early death. In addition to unpredictable and recurrent episodes of severe pain, commonly referred to as painful crises, a systemic vasculopathy leads to chronic and progressive tissue injury across multiple organ systems. Multiple pathophysiologic mechanisms likely contribute to the systemic vasculopathy, including, importantly, chronic hemolytic anemia (Rother, 2005).

On 25 November 2019, the United States (US) Food and Drug Administration (FDA) approved the study drug voxelotor, now known by the trade name OxbrytaTM. Oxbryta is indicated for the treatment of sickle cell disease in adults and pediatric patients 12 years of age and older.

In this trial, the Sponsor will be studying the risks and benefits of long-term treatment in participants previously treated in GBT440-031.

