ALT ≥5× and <8× ULN (confirmed by repeat testing within 48 to 72 hours) In the absence of additional signs of compromised liver function such as elevated PT, PTT, elevated conjugated bilirubin, jaundice, or hepatic pain.	Study drug: Reduce dose by one tablet. Additional actions: Repeat liver panel test within 48 to 72 hours if possible and then at least weekly until resolution to <5× ULN; if ALT test does not improve within 2 weeks of dose reduction, the Medical Monitor should be notified. If ALT continues to increase within 1 week after a dose reduction, dose should be interrupted, and the Medical Monitor should be notified.
Dose Interruption (Hold)	D 114.6
Event	Recommended Action
Grade 3 or higher AE that is (1) study drug - related in the opinion of the Investigator AND (2) that precludes continued dosing at the current or at a reduced dose level due to safety concern or lack of tolerability in the Investigator's judgment	Study drug: Hold dose until ≤Grade 2, then resume study drug at original dose. If, in the opinion of the Investigator, dosing should be resumed at a lower dose, contact the Medical Monitor. If the AE recurs or worsens, reduce dose by one tablet. Maximum dose hold is 5 continuous days. If, in the opinion of the Investigator, a longer dose hold is clinically needed, the Medical Monitor should be contacted for discussion.

Table 2. Dose Modification Guidelines for Study Drug-Related Adverse Events (Continued)

Drug Discontinuation	
Event	Recommended Action
Grade 3 or higher, study drug-related SAE	Study drug: Discontinue study drug. If the Investigator considers that the participant would benefit from continuing treatment, the Medical Monitor should be contacted for discussion.
Grade 3 or higher study drug-related AE that, at the discretion of the Investigator, warrants discontinuation of study drug (eg, has not improved or resolved after dose hold)	Study drug: Discontinue study drug. If the Investigator considers that the participant would benefit from continuing treatment, the Medical Monitor should be contacted
Consider treatment discontinuation if:	Study drug: Hold dose, confirm by repeat testing within 48 to 72 hours if possible, and assess for

Table 2. Dose Modification Guidelines for Study Drug-Related Adverse Events (Continued)

Drug Discontinuation	
Event	Recommended Action

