7.1.5.2. Blood Chemistry (Day 1 through Week 48)

Serum chemistry parameters are:

- alanine aminotransferase (ALT)
- alkaline phosphatase (ALK)
- aspartate aminotransferase (AST)
- bicarbonate,
- blood urea nitrogen (BUN)
- creatinine
- lactate dehydrogenase (LDH)
- Sodium
- Potassium
- Bilirubin (total, direct, and indirect)

Assessment of hematology and serum chemistry after Week 48 but should be performed per standard of care.

After Week 48, local laboratory assessments for Hb and measures of hemolysis will be performed by each site's local laboratory for participants enrolled outside of the United States and Europe. (Every 24 weeks)

- Hemoglobin
- % reticulocytes
- absolute reticulocytes
- Bilirubin (total, direct, and indirect)

7.1.5.3. Exploratory Measures Related to SCD Pathophysiology (Day 1, Weeks 12, 24, and 48)

function. CCI damage is a progressive complication of SCD that begins in childhood and may progress CCI. Assessments will be performed only for participants enrolled in the United States and Europe.

• CCI

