7.2.2.3. Abnormal Laboratory Values

Only clinically significant laboratory abnormalities as assessed by the Investigator will be recorded on the AE CRF (eg, abnormalities that have clinical sequelae, require study drug dose modification, etc.). If the clinically significant laboratory abnormality is a sign of a disease or syndrome (eg, ALK and bilirubin 5x ULN associated with cholecystitis), only the diagnosis (eg, cholecystitis) should be recorded as an AE on the CRF.

If the clinically significant laboratory abnormality is not a sign of a disease or syndrome, the abnormality itself, characterized by precise clinical term, as possible, should be recorded on the CRF (eg, elevated potassium of 7.0 mEq/L should be recorded as 'hyperkalemia').

Observations of the same clinically significant laboratory abnormality from visit to visit should not be repeatedly recorded on the AE CRF, unless their severity, seriousness, or etiology changes.

Note: Potential drug-induced liver injury (DILI; Hy's law) cases are to be reported as SAEs (Section 7.2.3). For suggested actions and follow-up assessments in the event of potential DILI, refer to Appendix 2. (This note is included to support Study transition to Pfizer Pharmacovigilance processes and systems.)

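### Appendix 2 requires no evidence of hemolysis for a potential Hy's law case, in a study where every participant has sickle cell disease, and does not exempt chronic SCD hemolysis

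*Protocol*

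**What the plan says.** Appendix 2 of the protocol sets the criterion for a potential DILI case. A participant with normal baseline values qualifies with AST/ALT of at least 3 × ULN and total bilirubin of at least 2 × ULN, "with no evidence of hemolysis and an alkaline phosphatase value < 2 × ULN or not available". For a raised baseline, the second bullet substitutes other AST/ALT and bilirubin limits into that same definition. It says nothing further about hemolysis.

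After repeat testing, cases that meet the enzyme and bilirubin criteria count as potential DILI "if no other reason for the LFT abnormalities has yet been found". Section 7.2.2.3 gives the consequence: "Potential drug-induced liver injury (DILI; Hy's law) cases are to be reported as SAEs".

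Section 1.6 limits the trial to participants with SCD. Section 1 describes that disease as "marked by the pathophysiologic features of hemolytic anemia, vaso-occlusion, and progressive end-organ damage" and calls the hemolytic anemia chronic. Neither the protocol nor the SAP defines evidence of hemolysis, gives a cut-off for it, or says whether a participant's usual SCD hemolysis should be disregarded.

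**The concern.** A no-hemolysis term guards against mistaking bilirubin from red-cell breakdown for liver injury. In a general population it excludes a few participants for a temporary reason. Here it describes the disease under study. A site that applies the words as written would reject a participant with evident SCD hemolysis however far AST, ALT and conjugated bilirubin had risen. A site that counts only new hemolysis would report the same participant as an SAE. About 100 sites are planned, so identical laboratory results could be handled in opposite ways.

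At stake is consistent reporting of the most serious liver signal in a study whose first objective is long-term safety.

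**Working it through.** The plan states no figure for this point, so the check is a logical one, with a short calculation for the bilirubin limb.

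**1. Structure of the definition.** A potential case requires all four of:
- (a) the AST/ALT limit is met;
- (b) the total bilirubin limit is met;
- (c) there is no evidence of hemolysis;
- (d) ALP is below 2 × ULN or not available.

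The raised-baseline bullet replaces the numbers in (a) and (b) only. Terms (c) and (d) carry over.

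**2. One participant, two readings.** The values are illustrative: normal ALT and total bilirubin of 2 × ULN at baseline; later ALT 5 × ULN, bilirubin up by 2 × ULN, ALP below 2 × ULN, and hemoglobin and reticulocytes at their usual SCD level.
- (a) 5 ≥ 3: met.
- (b) With raised baseline B, the limit is the smaller of B + 1 and 3, in × ULN. Here min(2 + 1, 3) = 3. The observed value is 2 + 2 = 4, and 4 ≥ 3: met.
- (d) Met.
- (c) If chronic SCD hemolysis counts as evidence, this fails and there is no potential case. If only new or worsened hemolysis counts, it is met, and the case is an SAE unless another reason is found.

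Only (c) separates the two outcomes. If (c) fails, no value of ALT or bilirubin can rescue the case.

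**3. Does other text settle (c)?**
- Appendix 2 says the laboratory threshold depends on baseline values and underlying conditions. That points towards the sensible reading but gives no rule for hemolysis.
- The limb for raised baseline bilirubin implies that such participants were meant to be able to qualify. It still works inside the same definition.
- The sentence on repeat testing names the enzyme and bilirubin elevations and not hemolysis, which again favours the sensible reading. Its closing condition, "if no other reason for the LFT abnormalities has yet been found", reopens the question, because SCD hemolysis is an obvious other reason for a raised bilirubin.
- Sponsor review is offered where uncertainty remains. It helps only if the site sees an uncertainty.

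None of these waives the term.

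**4. Where extra reports would arise once the term is reworded.** With limit T = min(B + 1, 3), the rise needed is T − B:

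| Baseline B (× ULN) | Limit T | Rise needed |
|---|---|---|
| 1.5 | 2.5 | 1.0 |
| 2 | 3 | 1.0 |
| 2.5 | 3 | 0.5 |
| 3 | 3 | 0 |

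Near or above 3 × ULN the bilirubin term asks for little or no rise, unless the word for reaching that level is itself taken to imply one. The documents give no distribution of baseline bilirubin, so these rows show the rule and not the expected numbers.

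**5. Are the measurements available?** Appendix 2 says liver tests are not routine in this study. Appendix 1 nevertheless schedules hematology and chemistry at Day 1, Weeks 12, 24 and 48 and End of Study (5 draws), plus Weeks 4 and 8 for some participants (7). Section 7.1.5.2 includes ALT, AST, ALK and fractionated bilirubin in the chemistry panel. After Week 48 the only scheduled full chemistry draw is End of Study.

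**The case against.** The strongest reply is that the literal reading is strained. It would largely empty an appendix added to this protocol by amendment for a study that enrols only SCD participants, and three pieces of Appendix 2 text lean the other way. That is fair, and many sites may read it sensibly without prompting. It remains an inference, because the operative definition keeps the term.

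A reader might go further and infer that liver injury in these participants would go unnoticed. The documents do not support that. Under Table 2 (Section 5.4), ALT above 3 × ULN with signs of compromised liver function, elevated conjugated bilirubin among them, calls for a dose hold, repeat testing within 48 to 72 hours if possible, a search for reversible causes and contact with the Medical Monitor. It has no hemolysis exclusion. (The table is headed as covering study drug-related events.) Clinically significant laboratory abnormalities are recorded as adverse events under Section 7.2.2.3, and an investigator can still judge an event medically important and therefore serious.

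A reader might also infer that raised bilirubin disqualifies a case by itself, because footnote f of Appendix 1 counts total and direct bilirubin among the hemolysis measures. On that reading nobody could qualify, even from a normal baseline, and Section 6.1 names unconjugated bilirubin as the hemolysis marker. The point should not rest on that footnote.

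Finally, no planned analysis depends on the criterion: the SAP has no DILI or Hy's law table. That is correct and limits the point to safety reporting.

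**Conclusion.** The point holds as a wording defect with a narrow effect. Applied literally, Appendix 2 removes participants with evident SCD hemolysis from Hy's law identification and from SAE reporting by that route. The surrounding text suggests this was not meant but does not correct it.

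The term applies to every participant, at most 274 by SAP Section 2.3. The documents do not give the share with evident hemolysis on voxelotor, the frequency of qualifying enzyme rises, or how sites read the term, so the number of affected cases cannot be derived. The conclusion assumes only that at least some sites take the words at face value. It does not show that any case has been missed, and it leaves dosing safeguards and the planned summaries untouched.

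**What to change.** Leave every AST/ALT, bilirubin and ALP threshold unchanged. In the definition, and so in both the normal-baseline and raised-baseline limbs, replace the hemolysis term with:

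*no evidence of new or worsened hemolysis, relative to the participant's pre-dose baseline in this study, that explains the bilirubin rise*

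Then add:

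*Chronic SCD hemolysis at the participant's usual level does not by itself exclude a case and is not by itself another reason for the abnormality; a rise in direct (conjugated) bilirubin supports a hepatic cause, but its absence does not exclude a case.*

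The baseline must be named because Section 6.1 uses two. The last clause matters because a waiver granted only when direct bilirubin rises would invite the converse, that chronic hemolysis does exclude when it has not risen.

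The cost is a short text change or equivalent written guidance to sites. Day 1 hemoglobin, reticulocytes and fractionated bilirubin give the comparison, and Appendix 2 already asks for direct and indirect bilirubin in suspected cases. Judging worsened hemolysis also needs current hemoglobin and reticulocytes, which a site would want for the existing term as well. The downside is some additional potential-DILI reports that work-up will explain, mainly where baseline total bilirubin is near or above 3 × ULN. Those reports still need the enzyme and ALP conditions, and Appendix 2 keeps confirmed status for cases where investigation has excluded another cause.
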